Apremilast in Combination with Clobetasol Spray for the Treatment of Plaque Psoriasis

INVESTIGATIONAL PRODUCT (IP): Apremilast and Clobetasol 0.05% spray

PROTOCOL NUMBER:

DATE FINAL:

EudraCT NUMBER:

IND NUMBER:

SPONSOR NAME / ADDRESS: [name] / [name]

MEDICAL MONITOR / EMERGENCY CONTACT INFORMATION

Name:	[name]
Title:	Principal Investigator/Sponsor Investigator
Address:	[name]
[contact]
E-mail:	[contact]

PROTOCOL SUMMARY

Study Title - Apremilast in Combination with Clobetasol spray for the treatment of plaque psoriasis of the body with or without scalp involvement

Indication – Apremilast is indicated for the treatment of patients with moderate to severe plaque psoriasis who are candidates for phototherapy or systemic therapy

Objectives

Primary Objective – Assessing the efficacy of combining Clobetasol spray with apremilast for the treatment of plaque psoriasis of the body with or without scalp

Secondary Objectives – Assessing the safety and quality of life in patients treated with Clobetasol spray and apremilast for the treatment of plaque psoriasis of the body with or without scalp

Study Design

Study Population- Adults 18 years and older with plaque psoriasis with at least 10% BSA involving the body with or without scalp lesions

Length of Study – 16 weeks

Study Treatments – Clobetasol is a superpotent topical corticosteroid. Many patients who use this may develop a rebound if stopped suddenly¹. Therefore, in this study the drug will be slowly tapered over 6 weeks. Patients with plaque psoriasis on the body with or without scalp involvement (not solely face/folds/hands/feet) begin apremilast at the approved psoriasis dosage. Patients will also begin clobetasol spray 0.05% to affected plaques bid for 2 weeks, then qday for 2 weeks then qod for 2 weeks then stop clobetasol but continue apremilast for a total of 16 weeks.

Overview of Efficacy Assessments – Patients will have BSA x PGA and PASI 75 scores measured at baseline then at 2, 4, 6, 8, 12 and 16 weeks. We will also record pruritus VAS and TSQM version II at all visits. If scalp involvement, we will also report scalp PGA

Primary Clinical Assessment- Proportion of patients achieving PASI 75 at Week 16 from baseline

Additional Clinical Assessments – Adverse Events (AE), Scalp PGA, Pruritus VAS, TSQM version II. Clinical Benefit, mean percent change from baseline in BSA x PGA at Week 16

Overview of Safety Assessments – Follow up visits initially then at 2,4,6,8 and 12 and 16 weeks.

1. INTRODUCTION

Approximately 30% of patients with psoriasis vulgaris achieve PASI 75 reduction at 16 weeks with oral apremilast. In a study using clobetasol spray as monotherapy twice daily for 4 weeks, 35.7% achieved clearance and 37.3% were almost clear. Potent topical steroids have the potential for adrenal suppression and skin atrophy with long-term use. For these reasons, they are ideal for inducing remission but not long-term use². The combination of clobetasol spray to induce rapid response with apremilast as a long-term treatment to maintain response may be a good treatment regimen.

1.1. Rationale for Dose Chosen

Apremilast dose as per FDA approval. Clobetasol spray given a slow taper over 6 weeks to reduce chance of skin flare.

1.2. Relevant Reference and Background:

In a survey conducted by the National Psoriasis Foundation from 2003-2011, 52.3% of patients reported dissatisfaction with their psoriasis treatments due to concerns about safety, tolerability or lack of efficacy².

The efficacy and safety of Apremilast was reported in 2 multicenter randomized, placebo-controlled phase 3 studies (ESTEEM 1 and ESTEEM 2). Apremilast demonstrated a significant increase in the proportion of patients achieving a PASI-75 response at week 16 in ESTEEM 1 (33.1% vs 5.3% in placebo) and in ESTEEM 2 (28.8% vs 5.8%)³.

Clobetasol 0.05% spray was found to be safe and effective in moderate to severe plaque psoriasis when used bid for 4 weeks in a single center, randomized, double blind study⁴.

2. STUDY OBJECTIVES

2.1. Primary Objective

Proportion of patients achieving PASI (Psoriasis area and Severity Index) 75 at Week 16 from baseline.

2.2. Secondary Objectives

Adverse Events (AE), proportion of patients with scalp psoriasis with improvement of ScPGA scores to 0 and 1 at Week 16, change from baseline in Pruritus VAS (Visual Analogue Scale) at Week 16, TSQM (Treatment Satisfaction Questionnaire for Medication) Version II. Clinical Benefit, mean percent change from baseline in BSA (Body Surface Area) x PGA (Physician Global Assessment) at Week 16.

3. OVERALL STUDY DESIGN

Open label, pilot trial with 20 patients with psoriasis vulgaris involving the body with or without scalp plaques

The study is designed as a 16-week study and consists of 8 visits as described in the table of events.

Screening

To reduce risk of gastrointestinal symptoms, titrate to recommended dose of 30 mg BID according to the following schedule:

- Day 1: 10 mg in morning
- Day 2: 10 mg in morning and 10 mg in evening
- Day 3: 10 mg in morning and 20 mg in evening
- Day 4: 20 mg in morning and 20 mg in evening
- Day 5: 20 mg in morning and 30 mg in evening
- Day 6 and thereafter: 30 mg twice daily

Weeks 0-2

Patients will receive apremilast 30 mg BID and clobetasol spray 0.05% to affected plaques BID for 2 weeks. The first week of IP dosing will consist of apremilast dose-titration card.

Weeks 2-4

Patients will receive apremilast 30 mg BID and clobetasol spray 0.05% to affected plaques once daily for 2 weeks

Weeks 4-6

Patients will receive apremilast 30 mg BID and clobetasol spray 0.05% to affected plaques every other day for 2 weeks, then stop clobetasol spray 0.05%

Weeks 6-16

Patients will continue to receive apremilast 30 mg BID

3.1. Data and Safety Monitoring Plan

Study Design Rationale

Approximately 30% of patients with psoriasis vulgaris achieve PASI 75 reduction at 16 weeks with oral apremilast. In a study using clobetasol spray 0.05% as monotherapy twice daily for 4 weeks, 35.7% achieved clearance and 37.3% were almost clear². Potent topical steroids have the potential for adrenal suppression and skin atrophy with long-term use. For these reasons they are ideal for inducing remission but not long-term use. The combination of clobetasol spray to induce rapid response with apremilast as a long-term treatment to maintain response may be a good treatment regimen.

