3.2. Study Duration- 16 weeks

4. TABLE OF EVENTS

Visit	Screening	Baseline	Apremilast Treatment					
	1	2	3	4	5	6	7	8
Week	Up to 7 days	0	2	4	6	8	12	16
Informed Consent	x							
Inclusion/Exclusion Criteria	x	x						
Medical and Disease History	x							
Height	x							x
Weight	x							x
Sex	x							
Race	x							
Prior/Concurrent Medications/Therapies	x	x	x	x	x ^a	x	x	x
Safety Assessments								
Pregnancy Test and Contraception Education for Females of Child- bearing Potential (FCBP)	x	x						x
Psoriasis Flare or Rebound Assessment	x	x	x	x	x	x	x	x
Adverse Events	x	x	x	x	x	x	x	x
Clinical Efficacy Assessments								
BSAxPGA	x	x	x	x	x	x	x	x
PASI	x	x	x	x	x	x	x	x
Pruritus VAS	x	x	x	x	x	x	x	x
Scalp PGA	x	x	x	x	x	x	x	x
TSQM version II	x	x	x	x	x	x	x	x
Investigational Product Dosing								
Dispense IP		x	x	x	x	x	x	x
Return IP tablets, Count for Compliance			x	x	x	x	x	x

^a Discontinue clobetasol spray 0.05% at Week 6

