10.5. Overdose

Abuse, withdrawal, sensitivity, or toxicity to an investigational product should be reported as an AE. Overdose, accidental or intentional, whether or not it is associated with an AE should be reported as an AE. Any sequela of an accidental or intentional overdose of an investigational product should be reported as an AE.

If the sequela of an overdose is an SAE, then the sequela must be reported on an SAE report form. The overdose resulting in the SAE should be identified as the cause of the event on the SAE report form but should not be reported as an SAE itself.

In the event of an overdose, the subject should be monitored as appropriate and should receive supportive measures as necessary. There is no known specific antidote for apremilast overdose. Actual treatment should depend on the severity of the clinical situation and the judgment and experience of the treating physician.

Overdose for this protocol, on a per dose basis, is defined as ingestion of any more than the amount prescribed of apremilast tablets in any 24-hour period whether by accident or intentionally.

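### Neither steroid risk named in Section 3.1 is actively assessed, and excess spray use outside abuse or toxicity has no explicit adverse-event rule

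*Combined protocol and SAP*

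**What the plan says.** The front page lists both drugs as study product: "INVESTIGATIONAL PRODUCT (IP): Apremilast and Clobetasol 0.05% spray". The Protocol Summary adds: "Clobetasol is a superpotent topical corticosteroid". Safety of the combination is a secondary objective there, and AEs head the list in Section 2.2.

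The section headed "3.1. Data and Safety Monitoring Plan" holds design rationale only. Its one safety statement is: "Potent topical steroids have the potential for adrenal suppression and skin atrophy with long-term use". It goes on to say that such steroids suit induction of remission rather than prolonged use.

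The Table of Events (Section 4) has three safety rows: pregnancy testing with contraception education, "Psoriasis Flare or Rebound Assessment", and adverse events. The last two are marked at all eight visits. No row covers skin atrophy, adrenal function, laboratory tests or physical examination. Section 10.1 allows AE monitoring to draw on laboratory or examination findings but requires none.

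Section 10.5 treats overdose of an investigational product as an AE. It then says that overdose, for this protocol, "is defined as ingestion of any more than the amount prescribed of apremilast tablets in any 24-hour period". The same section makes abuse of, and toxicity to, any investigational product reportable. Under Section 7.1.4, patients return spray bottles and are asked at each visit whether they used the spray as instructed. The check itself is worded as a tablet count, and the Table of Events compliance row refers to tablets.

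**The concern.** The protocol names two steroid harms and makes safety an objective, but it does not say how either harm would be found. Flare and rebound show the contrast: Section 5 defines both, and they have their own row at every visit. Atrophy and adrenal suppression have neither a definition nor a row.

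At stake is how a zero count would be read. If no case of atrophy is recorded, the report cannot separate patients who were checked and found clear from patients in whom nobody was prompted to check. For adrenal suppression without symptoms, a zero carries no information.

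The overdose definition adds a second gap. A spray cannot meet a definition based on ingesting tablets. Well-meant over-application, use on excluded sites or use after the scheduled stop may be neither abuse nor toxicity, and then no explicit rule makes it an AE. No amount of spray used is recorded that could show it another way.

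**Working it through.** The documents give no event rate, power or precision target for safety, so there is no plan figure to reproduce. Section 9.2 sets the sample size of about 20 on feasibility.

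**Step 1: named risk against scheduled check**

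| Risk | Where named | Scheduled check |
|---|---|---|
| Flare or rebound | Section 5 | Own row, all eight visits |
| Skin atrophy | Sections 1 and 3.1 | None; general AE row only |
| Adrenal suppression | Sections 1 and 3.1 | None; general AE row only |

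PASI, BSA and PGA require the examiner to look at the skin at all eight visits. PASI scores erythema, thickness and scaling. It has no item for atrophy, telangiectasia or striae.

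**Step 2: over-use**

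| Event | Apremilast | Clobetasol spray |
|---|---|---|
| Overdose as defined in 10.5 | Covered | Not covered |
| Abuse or toxicity (10.5) | Covered | Covered, terms undefined |
| Quantity check | Tablet count | None stated |
| Patient asked about use (7.1.4) | Yes | Yes |

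**Step 3: what zero cases in 20 would show**

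Exact two-sided 95% upper limit with perfect detection: 1 − 0.025^(1/20) = 16.8%.

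Let *s* be the chance that a true case is noticed and recorded. The documents do not give *s*, so these values are assumptions. The upper limit becomes 16.8%/*s*, computed from the unrounded 16.843%. For a true rate of 10%, the chance of recording no case is (1 − 0.10 × *s*)^20.

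| *s* (assumed) | Upper limit after 0/20 | Chance of 0 recorded if true rate is 10% |
|---|---|---|
| 1 | 16.8% | 0.90^20 = 12% |
| 0.5 | 33.7% | 0.95^20 = 36% |
| 0.25 | 67.4% | 0.975^20 = 60% |
| 0.1 | no rate excluded | 0.99^20 = 82% |

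The first row is the cost of having 20 patients. The rows below it are the cost of passive detection.

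**Step 4: planned exposure**

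Section 1.1 says: "Clobetasol spray given a slow taper over 6 weeks to reduce chance of skin flare". Section 7.1.1 gives twice daily, once daily and every other day, two weeks each: 14 × 2 + 14 × 1 + 14/2 = 28 + 14 + 7 = 49 applications. The clobetasol evidence in Section 1.2 is for the spray "when used bid for 4 weeks": 28 × 2 = 56 applications. Planned use lasts longer (6 weeks against 4) but involves fewer applications.

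**The case against.** The best defence is that the protocol limits the risk by design. It ties both harms to long-term use and then restricts the steroid to a six-week taper. It bars the face and folds, prohibits other topical corticosteroids, and excludes patients with steroid intolerance or uncontrolled endocrine disease. Planned applications are fewer than in the cited four-week evidence. An investigator examines the skin at every visit, including three visits after the spray stops at Week 6, and AEs are collected throughout. This is also a small open-label pilot with descriptive reporting.

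Most of this stands, and it rules out several stronger readings that a reader might infer:

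- *Spray over-use is never reportable.* Not supported. Abuse of, and toxicity to, any investigational product are AEs under Section 10.5, and spray use is queried at each visit. The gap is excess use that is neither.
- *The protocol does nothing about steroid risk.* Not supported. The measures above reduce risk. They do not detect harm, which is the narrower point here.
- *A zero count has no denominator.* Not supported. AEs are recorded for all subjects. What is unknown is the sensitivity of detection.
- *Six weeks means more exposure than the evidence covers.* Duration is longer, but the count of 49 against 56 does not show greater exposure.
- *The trial plans to claim that there was no steroid harm.* The documents plan no such statement. The issue is how a zero would be read under the safety objective.

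The defence does not supply a prompt to look for atrophy, any route to subclinical adrenal suppression, or an overdose definition that fits a spray.

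**Conclusion.** The point holds as a low-cost improvement. Neither risk named in Section 3.1 has a targeted assessment, and the overdose definition in Section 10.5 does not match the product definition on the front page. The primary endpoint is unaffected.

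The loss is in interpretation. The 16.8% limit for zero cases follows from 20 patients and perfect detection, and the fix does not improve it. The fix keeps the true uncertainty from being larger than that by an unknown amount. The figures of 33.7% and 67.4% rest on assumed detection of one half and one quarter. They illustrate the effect and are not estimates for this trial.

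The documents do not show that harm is likely under the planned taper, and this conclusion does not depend on that.

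**What to change.** 1. **Table of Events.** Add one line from Baseline to Week 16, completed by the same examiner during the PASI examination: steroid skin effects at treated sites (atrophy, telangiectasia, striae), present or absent. Enter new findings as AEs, and report the number of patients affected over the number examined.
2. **Section 10.5.** Reconcile it with the investigational product definition on the front page, so that reportable over-use also covers clobetasol use beyond the protocol's own schedule or sites. This changes no dose or treatment rule.
3. **Safety reporting.** State that adrenal suppression was not assessed and that no conclusion about it will be drawn.

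The cost is one extra case report form item at visits already scheduled and a short edit to the protocol text. There is no new visit, test or staff. The recorded AE count may rise slightly, because findings now left to chance would be entered.

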3.2. Study Duration- 16 weeks

4. TABLE OF EVENTS

Visit	Screening	Baseline	Apremilast Treatment					
	1	2	3	4	5	6	7	8
Week	Up to 7 days	0	2	4	6	8	12	16
Informed Consent	x							
Inclusion/Exclusion Criteria	x	x						
Medical and Disease History	x							
Height	x							x
Weight	x							x
Sex	x							
Race	x							
Prior/Concurrent Medications/Therapies	x	x	x	x	x ^a	x	x	x
Safety Assessments								
Pregnancy Test and Contraception Education for Females of Child- bearing Potential (FCBP)	x	x						x
Psoriasis Flare or Rebound Assessment	x	x	x	x	x	x	x	x
Adverse Events	x	x	x	x	x	x	x	x
Clinical Efficacy Assessments								
BSAxPGA	x	x	x	x	x	x	x	x
PASI	x	x	x	x	x	x	x	x
Pruritus VAS	x	x	x	x	x	x	x	x
Scalp PGA	x	x	x	x	x	x	x	x
TSQM version II	x	x	x	x	x	x	x	x
Investigational Product Dosing								
Dispense IP		x	x	x	x	x	x	x
Return IP tablets, Count for Compliance			x	x	x	x	x	x

^a Discontinue clobetasol spray 0.05% at Week 6

5. PROCEDURES

The following procedures will be conducted as outlined in the Table of Events.

Informed Consent

An Informed Consent Document will be signed by the subject before any study-related assessments are performed.

Contraception Education

The risks to a fetus or to a nursing child from apremilast are not known at this time. Results of the animal and in vitro studies can be found in the IB.

All females of childbearing potential (FCBP) must use one of the approved contraceptive options as described in section 4.2 while on investigational product and for at least 28 days after administration of the last dose of the investigational product.

When a female subject of childbearing potential's contraceptive measures or ability to become pregnant changes at the time of study entry or at any time during the study, the Sponsor Investigator will educate the subject regarding options and correct and consistent use of effective contraceptive methods in order to successfully prevent pregnancy.

Inclusion/Exclusion Criteria

Subjects must meet all inclusion criteria and must not have any of the conditions specified in the exclusion criteria to qualify for participation in the study. The subject's source documents must support his/her qualifications for the study (e.g., if a female subject does not require pregnancy testing and birth control because of a hysterectomy, the date of the hysterectomy must be included in the medical history).

Medical and Disease History

Relevant medical history should be recorded, including smoking and alcohol history, as well as previous relevant surgeries. Disease history includes history of psoriasis, psoriatic arthritis and chronic infections.

Prior/Concurrent Medications and Therapies

All medications and therapies being taken/used by the subject at the time of consent or at any time during the study will be recorded. Other key medications and therapies will be recorded.

Safety Assessments

The following assessments will be conducted as outlined in the Table of Events.

Psoriasis Flare and Rebound Assessments

Psoriasis flare is an AE (and will be recorded as an AE) and represents an atypical or unusual worsening of disease during treatment. It is defined as a sudden intensification of psoriasis requiring medical intervention or a diagnosis of new generalized erythrodermic, inflammatory, or pustular psoriasis. A more typical, gradual worsening of plaque psoriasis would not be recorded as an AE.⁵

Rebound is an AE and is defined as a severe and sudden worsening of disease that occurs after treatment has been discontinued. This exacerbation is characterized by a PASI \geq 125% of baseline or a new generalized pustular, erythrodermic or more inflammatory psoriasis after stopping therapy⁶.

Adverse Events

Details of AE reporting may be found in Section 10.

Clinical Efficacy Assessments

The following assessments will be conducted as outlined in the Table of Events, **Table 1**.

Psoriasis Area Severity Index (PASI)

PASI will be determined for all subjects throughout the study.

The PASI is a measure of psoriatic disease severity taking into account qualitative lesion characteristics (erythema, thickness, and scaling) and degree of skin surface area involvement on defined anatomical regions. The PASI is a validated instrument that has become standard in clinical trials for psoriasis.

Psoriasis Area Severity Index scores range from 0 to 72, with higher scores reflecting greater disease severity.⁷ Erythema, thickness, and scaling are scored on a scale of 0 (none) to 4 (very severe) on 4 anatomic regions of the body: head, trunk, upper limbs, and lower limbs. Degree of involvement on each of the 4 anatomic regions is scored on a scale of 0 (no involvement) to 6 (90% to 100% involvement). The total qualitative score (sum of erythema, thickness, and scaling scores) is multiplied by the degree of involvement for each anatomic region and then multiplied by a constant. These values for each anatomic region are summed to yield the PASI score.

Body Surface Area (BSA) x Physician Global Assessment (PGA)

BSA is determined by calculating the number of palms of psoriasis on the scalp and body. One palm of psoriasis represents 1% BSA. PGA is a 5-point scale from 0 (clear) to 4 (severe).

Scalp Physician Global Assessment (ScPGA)

ScPGA will assess scalp involvement, if present at baseline. ScPGA is a 6-point scale from 0 (clear) to 5 (very severe).

Visual Analog Scale (VAS) Assessments

The following assessments will be conducted as outlined in the Table of Events.

Pruritus Visual Analog Scale (VAS) Assessment

The subject will be asked to place a vertical stroke on a 100 mm VAS on which the left-hand boundary represents no itch, and the right-hand boundary represents itch as severe as can be imagined. The distance from the mark to the left-hand boundary will be recorded.

TSQM Version II

The subject will fill out a treatment satisfaction survey consisting of 11 questions on each visit.

6. STUDY POPULATION

6.1. Number of Subjects and Sites

One site and 20 patients

6.2. Inclusion Criteria

Subjects must satisfy the following criteria to be enrolled in the study:

1. Must be in general good health (except for disease under study) as judged by the Sponsor Investigator, based on medical history, and physical examination. (NOTE: The definition of good health means a subject does not have uncontrolled significant co-morbid conditions).
2. Females of childbearing potential (FCBP)[†] must have a negative pregnancy test at Screening and Baseline.
Option 1: Any one of the following highly effective methods: hormonal contraception (oral, injection, implant, transdermal patch, vaginal ring); intrauterine device (IUD); tubal ligation; or partner's vasectomy;
OR
Option 2: Male or female condom (latex condom or nonlatex condom NOT made out of natural [animal] membrane [for example, polyurethane]; PLUS one additional barrier method: (a) diaphragm with spermicide; (b) cervical cap with spermicide; or (c) contraceptive sponge with spermicide
3. Plaque psoriasis with at least 10% BSA involving the body with or without scalp lesions in adults aged 18 years and older.

[†] A female of childbearing potential is a sexually mature female who 1) has not undergone a hysterectomy (the surgical removal of the uterus) or bilateral oophorectomy (the surgical removal of both ovaries) or 2) has not been postmenopausal for at least 24 consecutive months (that is, has had menses at any time during the preceding 24 consecutive months).

[§] The female subject's chosen form of contraception must be effective by the time the female subject is enrolled into the study (for example, hormonal contraception should be initiated at least 28 days before baseline).

